### *Statistical Analysis Plan*

Data were analyzed on an intention-to-treat (ITT) basis, wherein participants were analyzed according to their treatment assignment by randomization, regardless of their compliance.

#### **Descriptive statistics, etc.**

Categorical variables were presented as percentages, continuous variables were presented as mean  $\pm$  standard deviation, medians and confidence intervals. Fisher's exact test was used to compare categorical variables between the two groups, while Mann-Whitney test was used to compare continuous variables between the two groups.

#### **Estimation of Treatment Effects**

##### *Continuous outcomes*

To investigate the treatment effects on continuous outcomes, we utilized Linear Mixed-effects Model (LMM) with random slopes. The treatment effects were estimated by modeling the interaction between time ( $T$ : after vs. before intervention) and the treatment arms ( $A$ : treatment vs. control). The specification of the models is provided below:

$$Y_{ij} = (\beta_0 + b_{0i}) + (\beta_1 + b_{1i}) * T_{ij} + \beta_2 T_{ij}^* A_i + \varepsilon_{ij}$$

Where:

$Y_{ij}|T, A, b_i \sim N(\mu, \sigma_y^2)$  is the study outcome of  $i^{th}$  individual at  $j^{th}$  measurement

$\beta_2$  is the treatment effect of interest

$b_i = (b_{0i}, b_{1i})' \sim N(0, D)$  are random intercepts and random slopes, respectively, with  $D$  unstructured variance-covariance matrix

$\varepsilon_{ij} \sim N(0, \Sigma)$  are the random errors, with  $\Sigma$  compound symmetry variance-covariance matrix

We constrained the baseline values of the outcome to be the same between the two arms in the model by omitting the group main effect (i.e., main effect of  $A$ ). This procedure is to gain efficiency of the model and is valid under randomization.

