to Clinical Dementia Rating). Participants receiving pharmacological treatment for dementia must be on a stable dose for at least 3 months prior to the study. Eligible participants must be able to mobilize independently with or without a mobility aid and without physical assistance.

Exclusion Criteria are

- ✓ Acute and malignant diseases (eg, advanced cancers, end-stage chronic diseases, acute myocardial infarction, stroke)
- ✓ Symptomatic cardiovascular disease or coronary revascularization within 1 year
- ✓ Clinical evidence of schizophrenia, severe depression, psychiatric or bipolar disorder (according to DSM-V TR criteria)
- ✓ Alcoholism or substance dependence (according to DSM-5 criteria), currently, or within the past 2 years
- ✓ Severe loss of vision, hearing or communicative ability (according to the interRAI Community Health Assessment)
- ✓ Participant or family unwilling to participate in the study.

Recruitment

Participants will be recruited from November 2022 until December 2023.

Research Team

The research team consists of 5 researchers, 2 research assistants, 2 neurologists and 2 physiotherapy experts. Prior to recruiting participants, the research assistants will complete a training program in screening and data collection using the specific measures to be used in the study.

Sample Size Estimates

Assuming a standardised effect sizes (ES) of 0.2 for a pilot randomised trial, with 90% power and two-sided 5% significance, and allowing for a 10% dropout rate and 5% mortality, the final sample size to be recruited is 60 (30 per study arm).

Randomisation, Concealment, and Allocation

A concealed, computer-generated sequence of randomly permuted blocks (block size = 4), stratified by age (60–69, 70–79, 80 and over) and disease severity (mild or moderate) will be generated by a statistician not otherwise involved in the study. Randomization will occur at the completion of the entire baseline assessment.

Blinding

Participants will be informed that they will be randomly assigned to one of the two treatment groups by the research assistants. Investigators will be blinded to the intervention allocation. All outcome measures will be administered by blinded assessors.

Study Procedure

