The study PI and/or researchers in the research team will contact adults aged 60 years and older in the nursing homes (Orihome, Nhan Ai, Dien Hong) to introduce the study. If they are interested in participating, the study PI and/or researchers in the research team will screen them for their eligibility. If they meet the inclusion criteria and are interested in participating, written informed consent will be obtained. Participants will be evaluated for capacity to give informed consent. If participants have the capacity to consent to the research project, they will receive a complete explanation of the purpose, risks, and procedures of the study and sign a written informed consent. Otherwise, a family member will consent for them.

A screening log will be kept to document number and reasons of participants who do not meet the inclusion criteria, decline to participate, or any other reasons.

Participants who agreed to participate in the study will be randomized into two equal groups, to receive either a multidomain intervention (intervention group) or regular health advice (control group). The intervention will include physical, cognitive, and social interventions, and management of metabolic and vascular risk factors.

The patients in the intervention group and the control group will be still participating in the usual care and activity, which were consistent across all three nursing homes in the study. The activities including quizzes and movement games will be held every 3 months. They will also be doing 15-minute morning exercise every day with light intensity. Participants in both the intervention and the control groups will be treated for dementia according to the recommendations of the Vietnam Alzheimer Disease and Neurocognitive Disorders Association.

All participants will meet the study physician to have an examination at baseline, 3 months and 6 months. At each examination, participants will undergo a physical examination, anthropometry (weight, and hip and waist circumference), blood pressure determination, pulse rate and rhythm check, assessment for cardiovascular risk factors and metabolic diseases (smoking, drinking, hypertension, coronary artery disease, dyslipidemia, atherosclerosis, diabetes) and assess blood test results (lipid profile, HbA1C and fasting glucose if patients have diabetes). Blood pressure measurements will be made on the left arm of the seated participants with a

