The primary outcome of the study is the feasibility of the intervention which will be assessed via the adherence and retention in intervention group.

Adherence: a count of sessions (percentage) attended out of the total planned

Retention: the number (percentage) of participants in each group who did not discontinue the study.

➤ Secondary Outcomes

Cognitive Function

Global cognition will be measured by Alzheimer's Disease Assessment Scale-Cognitive (ADAS-Cog), the Clinical Dementia Rating scale (CDR); executive function by the Clock test; and attention by digit span forward and digit span backward

Behavioral and Psychological Symptoms of Dementia (BPSD)

Researchers will interview care staff using the Neuropsychiatric Inventory (NPI) questionnaire.

Higher scores indicating greater severity

Functional ability will be assessed by using the Activities of Daily Living Scale (ADL), the Instrumental Activities of Daily Living Scale (IADL), handgrip strength and a 30 s chair stand test (30 s CST). The 30 s CST consists of counting the number of sit-stand-sit cycles completed during the 30 s test

Falls

Falls will be assessed by the fall incident report at baseline and during the study period.

Sleep Problem

Sleep Problem will be assessed with the Pittsburgh Sleep Quality Index. A global PSQI score over 5 indicates poor sleep

Health-Related Quality of Life

Health-related quality of life will be assessed with the Quality of Life in Alzheimer's Disease scale (QoL-AD). Total scores range from 13 to 52 with higher scores indicating higher quality of life.

Death

Death will be assessed through caregiver reports or nursing home records.

Ethical Approval and Consent

Ethical approval has been performed in accordance with the Declaration of Helsinki and have been approved from the National Geriatric Hospital (1139/IRB) on October 7, 2022. Participants will be evaluated for capacity to give informed consent. If participants have the capacity to consent

to the research project, they will receive a complete explanation of the purpose, risks, and procedures of the study and sign a written informed consent. Otherwise, a family member will consent for them. The trial is registered with ClinicalTrials.gov identifier: NCT04948450 registered on 02/07/2021.

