### **Handling missing values**

We applied direct likelihood method, which is valid under LMM, to address missing values for continuous outcome models.

For binary outcomes models, the Multiple Imputation by Chained Equations (MICE) method was employed. This algorithm created multiple imputed datasets based on a set of imputation models, assuming missing at random. We utilized logistic regressions as the imputation models for binary outcomes. The imputed model included the outcome variable and candidate predictors, including age, sex, marital status, education, and BMI. Due to small sample size, we could not impute all outcomes in the same model, therefore, each outcome was imputed separately. In total, 20 imputed datasets were created for each outcome. The estimates were estimated in each imputed dataset and then were pooled to obtain the single estimate based on Rubin's rules. We also compare the estimates based on multiple imputation to the results of available-case analyses.

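### Does the redundant covariance structure in the mixed model for continuous outcomes put the treatment effect at risk?

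*SAP*

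**What the plan says.** Under Continuous outcomes, in Estimation of Treatment Effects, the SAP says "we utilized Linear Mixed-effects Model (LMM) with random slopes", and the model equation gives each person a random intercept and a random slope. Time is binary, coded "after vs. before intervention". The fixed part has an intercept, time, and time by arm. There is no arm main effect, so the baseline mean is shared. The time-by-arm coefficient β2 is the effect of interest. The random effects have covariance D, an "unstructured variance-covariance matrix". The residuals have covariance Σ, a "compound symmetry variance-covariance matrix".

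On missing continuous data, Handling missing values says "We applied direct likelihood method, which is valid under LMM". The SAP text supplied does not name ML or REML, a degrees-of-freedom method, or a fallback if the fit fails.

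Four points in the protocol bear on this:
- Sample Size Estimates plans 60 participants, 30 per arm, "allowing for a 10% dropout rate and 5% mortality".
- Study Procedure has a physician "examination at baseline, 3 months and 6 months".
- Outcome Measurements lists the secondary scales without assigning any of them to the 3-month visit.
- The same section states: "The primary outcome of the study is the feasibility of the intervention".

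**The concern.** Two measurements per person have two variances and one covariance. The SAP describes these three quantities with five parameters, so infinitely many parameter sets fit equally well. A program may refuse such a model, fail to converge, or return no precision for the variance components. With no fallback in writing, the analyst would have to simplify after seeing the data.

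One obvious simplification is to drop the random slope. That forces equal variance before and after, and the standard error of β2 is wrong if the spread changes. The analyst might also use normal quantiles with about 30 people per arm, which is somewhat liberal. At stake would be the type I error and confidence intervals of the secondary continuous outcomes. The feasibility primary outcome is not touched.

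**Working it through.** The documents give no parameter count to reproduce, so the check starts from the model equation.

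**1. Inputs.** From the SAP: T = (0, 1); D with d11, d12, d22; Σ with variance part s² and common covariance c. From the protocol: 60 randomised and 10% + 5% = 15% lost. That leaves 60 × 0.85 = 51 with follow-up and 60 + 51 = 111 observations.

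**2. Count.** The marginal covariance is V = ZDZ′ + s²I + cJ, where J is a matrix of ones. Its elements are:
- V11 = d11 + c + s²
- V12 = d11 + d12 + c
- V22 = d11 + 2·d12 + d22 + c + s²

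These are three equations in five unknowns, and the Jacobian has rank 3. With a third occasion, at T = (0, 1, 1) or (0, 3, 6), the rank is 4 of 5, because c enters only through d11 + c. The redundancy is real.

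**3. What it leaves untouched.** The parameter sets (d11, d12, d22, s², c) below all give V = (100, 70, 160):

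| Set | V11 | V12 | V22 |
|---|---|---|---|
| (60, 10, 40, 40, 0) | 60+0+40 | 60+10+0 | 60+20+40+0+40 |
| (80, -10, 80, 20, 0) | 80+0+20 | 80-10+0 | 80-20+80+0+20 |
| (30, 10, 40, 40, 30) | 30+30+40 | 30+10+30 | 30+20+40+30+40 |

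On one simulated trial with some follow-up missing, all three gave REML log-likelihood -409.633, β2 = -2.788 and SE 2.869.

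**4. The written model reaches every admissible V.** Z is a 2x2 invertible matrix. For any positive-definite V, set c = 0, choose s² below the smallest eigenvalue of V, and take D = Z⁻¹(V - s²I)Z⁻ᵀ. This D is a valid covariance matrix. The five-parameter model and a single unstructured 2x2 covariance therefore describe the same family, with the same maximum, β2 and SE.

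**5. Numerical confirmation.** The five-parameter REML model was fitted as written to simulated data (60 people, 9 without follow-up) from six starting points. Across starts d11 ranged from 0.001 to 0.606 and c from -0.128 to 0.637. Every start gave V = (0.8107, 0.6468, 1.2504), log-likelihood -45.53453, β2 = -0.1279 and SE 0.2401, identical to the unstructured fit.

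**6. Does software break?** A standard mixed-model routine with a random slope and independent residuals (4 parameters, rank 3) was run on 200 simulated datasets. Standard errors of the variance components were undefined in all 200. The SE of β2 was defined in all 200, with no convergence warnings.

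**7. Degrees of freedom.** Var(β2) depends on the parameters only through V. Its gradient therefore lies in the row space of the information matrix, and the Satterthwaite quantity g′I⁻g does not depend on which generalised inverse is used. Three ways of computing it each gave 0.38795. The choice of reference distribution is a separate matter. At 49 df the 97.5% t quantile is 2.010 against 1.960, so using 1.96 gives about 5.6% on that account alone. In 20,000 simulated trials with 15% of follow-up missing completely at random, the unstructured model gave 6.08% with a normal reference and 4.92% with Kenward-Roger (Monte Carlo SE about 0.17 points).

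**8. The hypothetical fallback.** Type I error with the random slope dropped, at an assumed correlation of 0.6:

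| Follow-up SD / baseline SD (assumed) | Normal reference | Kenward-Roger |
|---|---|---|
| 0.8 | 3.17% | 2.73% |
| 1 | 5.59% | 4.88% |
| 1.25 | 8.48% | 7.54% |
| 1.5 | 10.76% | 9.68% |

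Neither the SD ratios nor the dropped slope comes from the documents.

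**The case for a change.** The best argument for a change is that it costs almost nothing. One unstructured 2x2 covariance, fitted by REML with a small-sample correction, says the same thing without redundancy. It runs in any package and removes discretion if a fit fails. The over-parameterisation is certain, a poor simplification could push type I error to 8.48% or 10.76%, and even a perfect fit is at 6.08% if normal quantiles are used.

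Part of this stands. The parameter count is right, and the single-matrix form is the cleaner way to write the model. The rest does not carry a change:
- Replacing the covariance leaves the estimate and its SE as they are.
- The 8% to 11% figures need the analyst to abandon the random slope that the SAP specifies, and the spread to grow by 25% to 50%. Dropping the redundant compound-symmetry term is just as easy and leaves β2 and its SE unchanged. The SAP is written in the past tense and mentions no failed fit.
- The 6.08% depends on a normal reference that the SAP does not state. It would apply in full to the cleaner model.
- The 3-month visit, as described, covers physical examination, anthropometry, blood pressure and blood tests. With time coded before and after, the SAP's model needs only two occasions.

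**Conclusion.** No change to the plan is called for. The SAP's covariance is redundant by 5 - 3 = 2 parameters, and its separate variance components have no unique values. No conclusion in the SAP text supplied rests on those components. The effect on β2 and its model-based SE, relative to an unstructured 2x2 fit, is zero. This assumes two occasions per person, as the SAP's coding of time says, and a fit that reaches the maximum.

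What remains is ordinary unstated detail: the reference distribution and the fallback. An analyst working on 60 people would normally use a small-sample t reference and remove the redundant term if a program objected. Naming the covariance and the degrees of freedom actually used belongs in the results report. If a normal reference had been used, type I error would be about 6.1% rather than 4.9%, given 15% of follow-up missing completely at random. That concerns secondary outcomes of a feasibility pilot and has nothing to do with the redundancy.

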##### *Binary outcomes*

For binary outcomes, the Generalized Estimating Equation models (GEE) were applied as our causal effects of interest are the population-average effects. The log link function was utilized to obtain the RR estimates. The specification of the models is provided below:

$$Y_{ij} \sim Bernoulli(\pi_{ij})$$

$$\log(\pi_{ij}) = \gamma_0 + \gamma_1 T_{ij} + \gamma_2 T_{ij}^* A_i$$

Where:  $\gamma_2$  represents the treatment effect of interest. We specified the exchangeable working assumption and obtained the empirical standard errors. The same constraint for baseline values, as mentioned in the LMMs, was applied.

### **Handling missing values**

We applied direct likelihood method, which is valid under LMM, to address missing values for continuous outcome models.

For binary outcomes models, the Multiple Imputation by Chained Equations (MICE) method was employed. This algorithm created multiple imputed datasets based on a set of imputation models, assuming missing at random. We utilized logistic regressions as the imputation models for binary outcomes. The imputed model included the outcome variable and candidate predictors, including age, sex, marital status, education, and BMI. Due to small sample size, we could not impute all outcomes in the same model, therefore, each outcome was imputed separately. In total, 20 imputed datasets were created for each outcome. The estimates were estimated in each imputed dataset and then were pooled to obtain the single estimate based on Rubin's rules. We also compare the estimates based on multiple imputation to the results of available-case analyses.

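### The SAP does not name randomised arm among the predictors for imputing binary outcomes; if arm was left out, a true effect shrinks by about the missing share

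*SAP*

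**What the plan says.** In the SAP, under Binary outcomes, the analysis model is a log-link GEE with an intercept, a time term and a time-by-arm term. The coefficient on time-by-arm, γ₂, "represents the treatment effect of interest". There is no main effect of arm, so baseline risk is held equal between arms and the whole arm contrast sits in the follow-up values.

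Under Handling missing values, binary outcomes are imputed by chained equations with logistic models, 20 datasets per outcome, assuming missing at random. The inputs are described as follows: "The imputed model included the outcome variable and candidate predictors, including age, sex, marital status, education, and BMI". The section adds: "Due to small sample size, we could not impute all outcomes in the same model, therefore, each outcome was imputed separately". It then says: "We also compare the estimates based on multiple imputation to the results of available-case analyses". It does not mention arm as a predictor or imputation within arm.

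Continuous outcomes take a different route: "We applied direct likelihood method, which is valid under LMM, to address missing values for continuous outcome models".

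The protocol's Sample Size Estimates section plans 30 participants per arm, "allowing for a 10% dropout rate and 5% mortality". The SAP does not list which outcomes are binary. Under Outcome Measurements the protocol gives one cut-off that could produce one: "A global PSQI score over 5 indicates poor sleep". Falls and death are also secondary outcomes.

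**The concern.** An imputation model should contain every variable in the analysis model whose association with the outcome is being estimated. Here that variable is arm, and the SAP names five covariates without naming it.

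If arm was absent, the imputed follow-up values carry no treatment effect: both arms' missing values are drawn from a blend of the two arms' risks. Nothing else in the named list repairs this. Age, sex, marital status, education and BMI, taken as baseline values, are independent of arm by randomisation. So is the baseline value of the outcome, if that is what the SAP means by the outcome variable. Because each outcome was imputed on its own, no other follow-up outcome can bring in arm information.

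At stake is a diluted estimate and lost power for binary secondary outcomes, in a pilot whose secondary objective is to look at effects. The feasibility primary outcome and the continuous outcomes are not affected.

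**Working it through.** The documents give no figure to reproduce, no event rates and no observed missing counts. Risks and missing shares below are therefore assumptions. The 10% and 15% cases correspond to the protocol's 10% dropout allowance, alone and with the 5% mortality allowance added. Data are taken as missing completely at random.

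**Closed form.** Let p_c and p_t be the true follow-up risks in control and intervention, m_c and m_t the missing shares, and the arms equal in size. An arm-blind model draws missing values at the pooled observed risk

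p̄ = [(1 − m_c)p_c + (1 − m_t)p_t] / [(1 − m_c) + (1 − m_t)],

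and each arm's risk after imputation is (1 − m)p + m·p̄, with that arm's own m and p.

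*Equal missingness, risks 0.50 and 0.30 (RR 0.60, log RR −0.511), p̄ = 0.40:*

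| Missing | Control | Intervention | RR | Log RR | Loss |
|---|---|---|---|---|---|
| 5% | 0.495 | 0.305 | 0.616 | −0.484 | 5% |
| 10% | 0.490 | 0.310 | 0.633 | −0.458 | 10% |
| 15% | 0.485 | 0.315 | 0.649 | −0.432 | 16% |

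For risks 0.50 and 0.40, a true RR of 0.80 becomes 0.809, 0.818 and 0.827. For true RRs between 0.5 and 2.0 the loss at 15% missing is 15.1% to 15.9%. It exceeds the missing share for extreme effects (20.1% at RR 0.20).

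*Unequal missingness, 15% overall, risks 0.50 and 0.30:*

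- All in control (m_c = 0.30, m_t = 0): p̄ = 0.65/1.70 = 0.382; control risk 0.35 + 0.30 × 0.382 = 0.465; RR = 0.30/0.465 = 0.646; loss 14.3%.
- All in intervention (m_c = 0, m_t = 0.30): p̄ = 0.71/1.70 = 0.418; intervention risk 0.21 + 0.30 × 0.418 = 0.335; RR = 0.335/0.50 = 0.671; loss 21.8%.
- A 2:1 split (20% and 10%): loss 14.5% with more missing in control, 17% with more in intervention.

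For risks 0.40 and 0.20, the two extreme splits give losses of 13.3% and 23.4%.

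**Large-sample check with the SAP's GEE** (log link, exchangeable, constrained baseline, robust standard errors; 20 imputations; 12 runs of 20,000). With risks 0.50 and 0.30, RR without arm is 0.633 at 10% missing and 0.647 at 15%; with arm it is 0.601 and 0.598. The closed form therefore carries over to the SAP's model.

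**At the planned size** (N = 60, 2,000 replicates, same risks; baseline outcome and the five named covariates in the imputation model):

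| | Without arm | With arm | Available-case |
|---|---|---|---|
| Rejection, 10% missing | 23% | 29% | 31% |
| Rejection, 15% missing | 18% | 27% | 29% |
| Rejection under no effect, 15% | 2.2% | 4.9% | 5.1% |
| Coverage, 15% | 0.960 | 0.957 | 0.957 |
| RMSE of log RR, 15% | 0.323 | 0.370 | 0.382 |

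Rejection with complete data is 34%. Mean log RR as a share of the complete-data value is 89% without arm and 98% with arm at 10% missing, and 83% and 97% at 15%. Adding arm widens the mean log-RR interval from 1.363 to 1.382 (1.4%) at 10% missing and from 1.379 to 1.416 (2.7%) at 15%.

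**Feasibility of the remedy** (separation of the logistic imputation model, 600 runs, N = 60, 10–15% missing):

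| Risks | By arm: control | By arm: intervention | Pooled with arm term |
|---|---|---|---|
| 0.50 / 0.30 | 10–15% | 33–37% | 0.2–0.5% |
| 0.40 / 0.20 | 18–21% | 57–63% | 0.5–2.2% |

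For a rarer outcome (0.30 and 0.18), the pooled model separates in 5.5–6.0% of runs with arm and 5.2% without.

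**The case against.** The strongest reply is that the omission is not established. The SAP introduces its covariates as examples, so arm may have been in the model, and the figures above may describe an analysis that was never run. That stands, and it is why the conclusion is conditional. What the text does show is that a reader cannot tell whether the imputation matched the analysis.

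The affected outcome is also uncertain. Most secondary outcomes are scales or counts that suit the mixed model. Falls and death come from reports or records and may have few missing values. The sleep cut-off is only a candidate. With nothing missing, or no true effect, there is no bias. The 15% case further assumes that deaths count as missing and are imputed, which the SAP does not say. Missing values all in one arm would mean 30% missing there and none in the other, which nothing in the documents suggests.

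The effect is small beside sampling error. The shift at 10% missing is about 0.05 on the log scale (0.511 − 0.458), coverage is not harmed and RMSE is lower without arm. The direction is conservative. All true; but the lower RMSE comes from shrinking toward no effect, and the price is bias and power.

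Finally, the planned available-case comparison is free of this bias under data missing completely at random. It is a real safeguard but a partial one: at 60 participants chance can hide or mimic the difference, and the SAP does not say which estimate is the main result.

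**Conclusion.** The point holds as a minor, conditional one. The SAP does not name arm in the imputation of binary outcomes and does not otherwise show that it was used. If the named predictors were the whole model, a true log RR shrinks by about the missing share when missingness is equal by arm: RR 0.60 becomes 0.62, 0.63 and 0.65 at 5%, 10% and 15% missing. With unequal missingness at 15% overall, the loss ranges from about 13% to 23% in the cases examined. Power at 60 participants falls by 6 points at 10% missing (29% to 23%) and 9 points at 15% (27% to 18%), relative to imputing with arm.

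These sizes rest on assumed risks, assumed missing shares and data missing completely at random. The consequence is attenuation and lost power for binary secondary outcomes, not false benefit.

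**What to change.** State whether randomised arm and the baseline value of the same outcome were in each binary-outcome imputation model. If arm was absent, add it, together with the baseline value, to one pooled logistic model per outcome, drop a weaker covariate where events are few, and rerun. Imputing separately by arm is not advised with about 30 per arm, because separation was frequent under the assumed risks. Name the arm-inclusive imputed estimate as the main result and the available-case estimate as the sensitivity analysis. This fits the SAP, which presents available-case only as a comparison, although available-case performed about as well in the simulation; what matters is that the choice is stated. Report missing counts by arm for each binary outcome.

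The cost is one or two sentences in the SAP, a small change to the imputation code and a rerun, with no new data. The statistical price is one or two more terms per model at N = 60 and intervals 1.4% to 2.7% wider in the cases above. The gain is less bias and more power, not lower RMSE. If arm was already included, one clarifying sentence about the imputation model settles the bias question.
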